## 1.4. Study Structure

- Screening will be done within 21 days prior to Day 1 (the first injection of study drug). See [Section 9.2](#) for details of screening and [Section 9.3](#) for details of the enrollment process.
- Treatment is scheduled to be administered in 8-week cycles until progressive disease, unacceptable toxicity, withdrawal of consent, or end of study.
- Assessments for treatment response (or disease progression) are scheduled every 8 weeks  $\pm$  1 week (at the start of a new cycle) for clinical assessments (see [Section 9.4.1](#)), and every 4 weeks  $\pm$  1 week for laboratory assessments (see [Section 9.4.2](#)).
- End-of-Treatment (EOT) visit will be performed within 5 days of the decision to terminate treatment.
- End-of-Study (EOS) visit will be performed 30 to 35 days after the last dose of study drug.

A detailed schedule of events is presented in [Table-4](#).

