### **1.7.3. *Treatment Effect***

Assessments of disease status will be conducted at Screening, every 4 weeks  $\pm$  1 week (Week 1 and Week 5 of each cycle; for laboratory assessments, see [Section 9.4.2](#)), every 8 weeks

± 1 week (Week 1 of each cycle; for clinical assessments, see [Section 9.4.1](#)), every 12 weeks ± 4 weeks during the Follow-up Phase, at the EOT visit, and at the EOS visit. Disease assessments will be classified based on the guidelines of the VIth International Workshop [1]. Time to progression and duration of response will be measured as defined. See [Section 9.5](#) for details. Patients discontinued from the study for reasons other than progressive disease will be assessed at a minimum of every 12 weeks ± 4 weeks until documentation of progressive disease, initiation of a subsequent anti-cancer therapy, or until the study ends, for up to 6 months from the first treatment (Cycle 1, Day 1) for the last patient enrolled, whichever comes first.

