Abbreviations: AE=adverse event; CT=computed tomography; ECG=electrocardiogram; ECOG=Eastern Cooperative Oncology Group; EOS=end-of-study; EOT=end-of-treatment; F/U=Follow-up; IgM=immunoglobulin M; NF- $\kappa$ B=nuclear factor kappa-light-chain-enhancer of activated B cells; PK=pharmacokinetic; MRI=magnetic resonance imaging; Scrn=Screening; WM=Waldenström's macroglobulinemia

 Day 1 is the day of the first injection of study drug. All weeks for a given cycle are relative to the day of the first injection of study drug for that Cycle and are defined as Day 1 through Day 7, inclusive; all times are relative to injection, designated 0 hour; “pre-dose” vital signs are to occur within 1 hour prior to injection; all other pre-dose procedures are to occur prior to injection on the same calendar day.

 Screening procedures may be performed up to 21 days prior to Day 1.

 If treatment is terminated prematurely for any reason, the EOT visit will be performed within 5 days of the decision to terminate; the EOS visit will be performed 30 to 35 days after the last dose of study drug.

 Informed consent must be signed prior to all study-specific screening procedures.

 Medical history includes, but is not limited to, a detailed review of the patient’s malignancy, prior treatments, relevant current or past abnormalities or diseases, and signs and symptoms of WM at baseline.

 Cryoglobulin and cold agglutinin laboratory testing to be performed at Screening (local laboratory).

 To occur pre-dose.

 During Cycle 1 only, physical examination will be done on Week 2. In subsequent cycles, physical examinations will be done every 4 weeks.

 Vital signs comprise heart rate, blood pressure, respiratory rate and temperature. Vital signs will be obtained pre-dose (within 1 hour prior to injection) and post-dose at 30 ( $\pm$  5) min after dosing. On Day 1 of Cycle 1, Week 1, post-dose vital signs will also be obtained at 2 hours ( $\pm$  20 min).

 For patients who receive a second weekly dose, vital signs will be obtained pre-dose (within 1 hour prior to injection) and post-dose at 30 ( $\pm$  5) min after dosing, and assessment of the injection site, as previously noted, will be conducted.

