 Clinical assessment for tumor status will be conducted pre-dose on dosing visits and will include assessment for lymphadenopathy, hepatomegaly, and splenomegaly (see [Section 9.4.1](#) for details).

 Assessments will be conducted pre-dose on dosing visits, and includes total serum IgM, monoclonal serum IgM, serum free light chains, urine free light chains, serum viscosity, and serum  $\beta$ 2-microglobulin; see [Section 9.4.2](#) for details.

 CT or MRI imaging of chest, abdomen, and pelvis with the same modality used for every assessment; see [Section 9.4](#) for details.

 The full panel of safety laboratory tests (hematology, serum complement, chemistry and coagulation) will be done pre-dose on Day 1, and Weeks 1 and 5 of each cycle (including pre-treatment criteria presented in [Section 8.4.1](#)); a focused panel (hematology, selected chemistry) will be done pre-dose on Weeks 3 and 7 of each cycle; see [Section 9.7.1](#) for details. Unscheduled tests to confirm decreases in serum complement levels will be performed (see [Section 6.5.4](#)).

 ECGs are to be performed pre-dose and 2 hours post-dose on Day 1 of Cycle 1 and pre-dose at the first dosing visit of Weeks 1 and 5 of each cycle thereafter. In addition, an ECG is to be performed at 2 hours post-dose on Day 1 of each odd-numbered cycle.

 Serum pregnancy testing will be done pre-dose and evaluated at the central laboratory.

 PK samples will be collected as scheduled in relation to the first dose administered on Day 1 of every cycle. Samples will be obtained pre-dose (within 1 hour prior to injection) and post-dose at 1 hour ( $\pm$  5 min), 2 hours ( $\pm$  10 min) and 4 hours ( $\pm$  15 min) after dosing. PK samples will also be taken at EOT and EOS.

 Serum for cytokines and antibodies to IMO-8400 will be collected as scheduled in relation to the first dose administered on Day 1 of every cycle and will be obtained pre-dose (within 1 hour prior to injection).

 Serum samples for NF- $\kappa$ B analysis will be obtained pre-dose (within 1 hour prior to injection) and post-dose at 4 hours ( $\pm$  15 min) (see [Section 9.9](#) for details) and will be submitted to central laboratory.

 Bone marrow slides will be obtained from initial WM diagnosis.

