## 6.5. Management of Individual Patients

### 6.5.1. Duration of Treatment

Each enrolled patient will receive IMO-8400 at the assigned dose level until the earliest of:

- *Clinical DLT event* – see [Section 6.3](#).
  - Study treatment will be discontinued in patients determined to have a clinical DLT event until resolution and may only be resumed after discussion with an Idera Medical Monitor and agreement that it is in the patient's best interest to continue.
  - For a DME, provision is made for interrupting dosing for up to 3 weeks and, if the acute toxicity improves sufficiently, resuming treatment at a lower dose level based on discussion between the sponsor's designated medical monitor and the treating physician.
  - For DLT laboratory events, provision is made for pausing treatment for up to 3 weeks and, if the acute toxicity improves sufficiently, resuming treatment at a lower dose level (see [Section 6.5.2](#) for details).
  - The Investigator will review with the Medical Monitor decisions to discontinue, pause, and/or restart study treatment.
- *Disease progression* – based on scheduled assessments at Week 1 of each cycle. Unscheduled assessments may be conducted in response to new clinical observations. Disease status will be classified according to international guidelines [1] (see [Section 9.5](#) for details).
- *Termination of participation in the study* – due to AE, withdrawal of consent, intolerable toxicity, or loss to follow up.

In certain instances, patients may be deriving clinical benefit despite objective signs of progressive disease such as radiologic progression. It can be anticipated that based on the study drug's mechanism of action, through an immunologic mediated effect, signs of radiologic response may be delayed. Based on these considerations, continuing to treat some patients past progressive disease may be considered after discussion between the Sponsor and Investigator, provided the following conditions are met:

- Patient has not achieved an objective response on study and then developed progressive disease;

- Patient has not experienced a period of clinically significant stable disease on study and then developed progressive disease;
- Patient must be re-evaluated 4 to 6 weeks after initial progression in order to confirm progressive WM disease;
- If the follow-up assessment does not confirm progressive disease, patient may resume regularly scheduled follow-up per protocol;

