### **9.4. Assessments of Waldenström's Macroglobulinemia**

Laboratory assessments for disease status (see [Section 9.4.2](#)) will be conducted at Screening, every 4 weeks  $\pm$  1 week (Week 1 and Week 5 of each cycle), every 12 weeks  $\pm$  4 weeks during the Follow-up Phase, at the EOT visit, and at the EOS visit.

Clinical assessments for disease status (see [Section 9.4.1](#)) will be conducted at Screening, every 8 weeks  $\pm$  1 week (Week 1 of every cycle), every 12 weeks  $\pm$  4 weeks during the Follow-up Phase, at the EOT visit, and at the EOS visit.

Radiologic imaging will be performed at Screening and at EOT visit or as clinically indicated.

Bone marrow biopsy and aspirate will be performed at Screening, EOT, and to document complete response as appropriate (see [Section 16.2](#)).

A medical history specific to WM will be collected at Screening and will include, but is not limited to: a detailed review of the patient's malignancy, prior treatments, relevant current or past abnormalities or diseases, and signs and symptoms of WM at baseline ([Section 9.6.1](#)).

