#### 12.4.1.2. Secondary Treatment Effect Parameters

The VIth International Workshop specifies a number of outcome metrics related to time [1] (see [Section 16.3](#)). The following parameters are considered most relevant to this time-limited study and will be analyzed both globally across all cohorts and by dose level.

- Distribution of response categories by treatment group and overall.
- Time to progression – Time from the initiation of treatment to disease progression with deaths due to unrelated causes censored.
- Progression-free survival – Time from the initiation of treatment to disease progression or death from any cause.
- Time to best observed response – Time from the initiation of treatment to best observed category of response.

- Percent and absolute change in quantitative serum levels of monoclonal and total IgM.

Kaplan-Meier analyses will be used to analyze time to event data. Analysis of IgM data will be performed using a repeated measures mixed model. MyD88 L265P mutation status will be used as a covariate in statistical analyses.

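### Disease-assessment weeks are tied to each cycle's first injection, so a dose hold that delays a cycle start by more than 7 days can push IgM and clinical assessments outside their stated windows

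*Protocol*

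**What the plan says.** **Dosing-based clock.** Table 4, footnote 1: "All weeks for a given cycle are relative to the day of the first injection of study drug for that Cycle". The same footnote puts pre-dose procedures other than vital signs on the calendar day of the injection. Footnote 11: "Clinical assessment for tumor status will be conducted pre-dose on dosing visits". Footnote 12 does the same for total and monoclonal IgM.

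**Interval-based clock.** Section 1.4: "Assessments for treatment response (or disease progression) are scheduled every 8 weeks", with a window of 1 week either side for clinical assessments, and every 4 weeks with the same window for laboratory assessments. Sections 1.7.3, 9.4 and 12.4.1 repeat these intervals and equate them with cycle weeks. Section 1.7.3 has "1 week (Week 1 of each cycle; for clinical assessments" and Section 9.4 has "Week 1 and Week 5 of each cycle), every 12 weeks". The equation works on plan, because Section 1.4 states "Treatment is scheduled to be administered in 8-week cycles".

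**Holds.** For laboratory DLTs, Section 6.5.1 says "provision is made for pausing treatment for up to 3 weeks", and it allows the same for dose modifying events. Sections 6.5.2 and 8.4.2 let a toxicity interruption run beyond 21 days by agreement. The complement and platelet holds in Sections 6.5.4 and 6.5.5 carry no time limit of their own. Section 8.4.1 checks the pre-treatment laboratory criteria at Weeks 1 and 5, the weeks in which IgM is drawn.

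**Use of the data.** Section 12.4.1.2 lists time to progression, progression-free survival, time to best response and change in IgM, which "will be analyzed both globally across all cohorts and by dose level".

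**The concern.** The interval-based and dosing-based clocks coincide only if every cycle starts close to plan. The pre-treatment check falls in Week 1, so a hold can land on the injection that defines the cycle. If the site follows footnote 1, Week 1 and its assessments wait for resumption. If it follows the intervals, they do not wait. No section says which rule prevails, or that disease assessments continue during a hold, so sites could reasonably differ.

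At stake is when progression and response can be observed. Section 6.5.1 reads progression from the scheduled Week 1 assessments, so a patient held and later resumed may be assessed late and have progression dated late. The repeated-measures IgM model would take its samples at times that depend on toxicity. This is a data-collection rule. An SAP can set windows and censoring, but it cannot recover a sample that was not drawn.

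**Working it through.** **Inputs (Protocol)**
- Cycle length 8 weeks (Section 1.4).
- Clinical assessment at Week 1, window 8 ± 1 weeks; IgM at Weeks 1 and 5, window 4 ± 1 weeks (Sections 1.4, 1.7.3, 9.4).
- Cycle weeks counted from the cycle's first injection (Table 4, footnote 1).
- Pause of up to 3 weeks (Section 6.5.1) and a 21-day limit, extendable (Sections 6.5.2, 8.4.2). The day from which these are counted is not stated, so both readings are shown.
- Laboratory recovery within 14 days of the last dose as a condition for resuming after a laboratory DLT or dose modifying event (Section 6.5.2).

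**Day numbers, once-weekly dosing, Cycle 1 Day 1 = Day 1**
- Week 5 IgM draw: 1 + 28 = Day 29.
- Last Cycle 1 dose (Week 8): 1 + 49 = Day 50.
- Planned first Cycle 2 injection: 1 + 56 = Day 57.

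If the first Cycle 2 injection falls on Day D, and the preceding assessments were on time:
- clinical gap = (D − 1)/7 weeks, at most 9 to be in window;
- IgM gap = (D − 29)/7 weeks, at most 5 to be in window.

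| First Cycle 2 injection | D | Slip (days) | Clinical gap (weeks) | IgM gap (weeks) | In window? |
|---|---|---|---|---|---|
| On plan | 57 | 0 | 56/7 = 8.0 | 28/7 = 4.0 | yes |
| Allowed 2-day variance | 59 | 2 | 58/7 = 8.3 | 30/7 = 4.3 | yes |
| 14 days after last dose | 64 | 7 | 63/7 = 9.0 | 35/7 = 5.0 | at the edge |
| 21 days after last dose | 71 | 14 | 70/7 = 10.0 | 42/7 = 6.0 | no |
| 28 days after last dose (21 after the planned dose) | 78 | 21 | 77/7 = 11.0 | 49/7 = 7.0 | no |

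The first row reproduces the protocol's 8 and 4 weeks. Both windows break once the cycle start slips by more than 7 days.

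**Detection delay.** Assume progression is equally likely at any time between two assessments. Mean delay to detection is then gap/2.
- Clinical: 8/2 = 4.0 on plan; 10/2 = 5.0 and 11/2 = 5.5 in the two breaching cases.
- IgM: 4/2 = 2.0 on plan; 6/2 = 3.0 and 7/2 = 3.5 in the two breaching cases.

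The increase is 1.0 to 1.5 weeks, and it applies to the one lengthened interval. Once dosing is regular again, spacing returns to 8 and 4 weeks and mean delay to 4 and 2 weeks, even though later visits remain offset from the calendar.

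**With a calendar anchor.** Gaps stay at 8 ± 1 and 4 ± 1 weeks for any hold.

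**The case against.** The best defence is that footnotes 11 and 12 fix only the order of procedures within a visit at which a dose is given. Table 4 schedules the same assessments at Screening and EOS, where no dose is given, and nothing forbids an IgM draw or node examination when the dose is withheld. The laboratory check also precedes the injection, so when a hold is decided at the planned Week 1 visit the disease assessments may already have been done on time. This reading is possible, so the two rules are not always impossible to satisfy together. It does not remove the anchor stated in footnote 1, and the protocol does not say whether assessments at a visit without an injection count or must be repeated.

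Several limits on the size stand. A slip of 7 days or less stays in window. A mid-cycle hold that ends before the next cycle is due need not move that cycle's start. Section 6.5.2 bars resumption after a second hold for a laboratory DLT or dose modifying event, so only other holds could recur. Section 9.1 also does not carry the cycle-injection anchor: it counts days from the first study injection and weeks from Week 1 of each cycle.

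Two safeguards exist but are partial. Unscheduled assessments are optional and prompted by new clinical observations, so they may miss an asymptomatic rise in IgM. The EOT visit, within 5 days of a decision to stop, covers termination but not a hold followed by resumption.

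A reader might infer that detection is delayed most at the most toxic doses, flattering them. The documents do not support that as a finding. They give no hold rates by dose level, Section 4.4.1 reports general tolerability at the levels then tested, and toxicity that ends treatment leads to a prompt EOT assessment.

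**Conclusion.** The point holds in a limited form. Footnote 1, read with footnotes 11 and 12, lets disease assessments follow dosing, and permitted holds can then take them outside the windows stated elsewhere. The gap reaches 10/6 or 11/7 weeks (clinical/IgM) when dosing resumes 21 or 28 days after the last dose, and only the edge of the window (9/5) at 14 days. The 11/7 figure is the upper case among these, not the typical one. An interruption extended by agreement could exceed it.

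The extra mean detection delay is at most 1.0 to 1.5 weeks in these cases, for a single interval. It rests on uniform progression between visits, on-time preceding assessments, once-weekly dosing, and a site that waits for the injection. A persistent calendar offset should not be read as accumulating delay.

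The effect falls on secondary treatment-effect parameters in an uncontrolled study whose primary objective is safety. By-dose comparisons could be biased if holds differ by dose level, but neither the direction nor the size can be computed from the protocol. The response-rate power statement in Section 12.1 uses no assessment-interval input and is unaffected. The change is still worth making, because it is cheap and takes dosing-dependent timing out of these data.

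**What to change.** In Table 4, footnotes 1, 11 and 12, state that total and monoclonal IgM are assessed every 4 ± 1 weeks, and clinical tumor status every 8 ± 1 weeks, in calendar weeks from Cycle 1 Day 1, whether or not a dose is given. Add that an assessment done at a planned visit where the dose is then withheld counts as that scheduled assessment.

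Carry the same rule through Sections 1.7.3, 6.5.1 (and its synopsis counterpart, 1.3.7), 9.1, 9.4 and 12.4.1, which refer to cycle weeks. Editing the footnotes alone would leave new contradictions. Dosing, the hold rules, PK sampling and dose-related safety procedures stay on the cycle clock and are not touched.

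The cost is a short wording change in several places. A patient on hold may need a blood draw and a node and organ examination at the calendar time instead of at resumption. The planned assessment frequency does not change.

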**Table-5. Estimation of Blood Volumes Required From Screening through End-of-Study**

Tests	Volume (mL)	Screening (mL)	Maximum Volume Per 8-week Cycle (mL)	EOT (mL)	EOS (mL)
Safety Lab Tests (full)	19	19	38	19	19
Safety Labs (focused)	10		20		
PK	2		8	2	2
Serum Cytokines	4	4	4	4	4
Antibodies to IMO-8400	4	4	4	4	4
Serum NF-κB	10		20	10	10
Tumor Assessments	15	15	30	15	15
Pregnancy test (F only) (extra blood volume is not required)	X	X	X	X	X
Serology	10	10			
Total mL blood drawn		52	124	54	54

Abbreviations: EOS=end-of-study; EOT=end-of-treatment; F=female; NF-κB=nuclear factor kappa-light-chain-enhancer of activated B cells; PK=pharmacokinetic

Note: The volumes shown are estimates; final volumes may vary, but will not be more than 15% greater than shown.

### 3. LIST OF ABBREVIATIONS

Abbreviation	Explanation
ABC-DLBCL	Activated B-cell (type) Diffuse Large B-cell Lymphoma
AE	Adverse event
ALT	Alanine amino-transferase
AP	Alkaline phosphatase
aPTT	Activated partial thromboplastin time
AST	Aspartate amino-transferase
β-hCG	Beta-human chorionic gonadotropin
BA	Bioavailability
BCR	B-cell receptor
BE	Bioequivalence
BP	Blood pressure
BTK	Bruton's tyrosine kinase
C3	Complement component 3
C4	Complement component 4
CBC	Complete blood count
CFR	Code of Federal Regulations
CH50	50% hemolytic complement assay
CK	Creatine phosphokinase
CNS	Central nervous system
CR	Complete response
CRP	C-reactive protein
CS	Clinically significant
CSR	Clinical Study Report
CT	Computed tomography
DLBCL	Diffuse large B-cell lymphoma
DLT	Dose-limiting toxicity
DME	Dose modifying event
DNA	Deoxyribonucleic acid
DRC	Data Review Committee
ECG	Electrocardiogram
ECOG	Eastern Cooperative Oncology Group
eCRF	Electronic case report form
EDC	Electronic data capture
EE	Efficacy Evaluable
EHR	Electronic Health Record
EOS	End-of-study
EOT	End-of-treatment
FDA	Food and Drug Administration (US)
GCP	Good Clinical Practice
GMP	Good Manufacturing Practice
HBsAg	Hepatitis B surface antigen
HCV	Hepatitis C virus
HDL	High density lipoprotein
HIV	Human immunodeficiency virus

---

HR	Heart rate
ICF	Informed consent form
ICH	International Council for Harmonisation
IEC	Independent ethics committee
IFN	Interferon
IgM	Immunoglobulin M
IL	Interleukin
IND	Investigational new drug
INN	International nonproprietary name
INR	International normalized ratio
IP-10	Interferon-inducible protein-10
IRB	Institutional Review Board
ISR	Injection site reaction
ITT	Intent-to-treat
LDH	Lactate dehydrogenase
LDL	Low density lipoprotein
MCH	Mean corpuscular hemoglobin
MCHC	Mean corpuscular hemoglobin concentration
MCV	Mean corpuscular volume
MTD	Maximum tolerated dose
MyD88	Myeloid differentiation primary response gene (88)
MR	Minor response
MRI	Magnetic resonance imaging
NA	Not applicable
NCI CTCAE	National Cancer Institute Common Terminology Criteria for Adverse Events
NF- $\kappa$ B	Nuclear factor kappa-light-chain-enhancer of activated B cells
NCS	Not clinically significant
PP	Per-protocol
PR	Partial response
PK	Pharmacokinetic(s)
PT	Prothrombin Time
RBC	Red blood cell
RNA	Ribonucleic acid
RP2D	Recommended Phase 2 dose
SAE	Serious adverse event
SAP	Statistical Analysis Plan
SC	Subcutaneous
SUSAR	Suspected unexpected serious adverse reaction
TEAE	Treatment-emergent adverse event
TLR	Toll-like receptor
TMF	Trial master file
TNF	Tumor necrosis factor
ULN	Upper limit of normal
USP	United States Pharmacopeia
VGPR	Very good partial response
WBC	White blood cell
WM	Waldenström's macroglobulinemia
WMA	World Medical Association

---

## 4. INTRODUCTION

### 4.1. Waldenström's Macroglobulinemia (WM): the Disease under Study

Hematological malignancies are cancers affecting blood, bone marrow, and lymph nodes; they may derive from either myeloid or lymphoid cell lines. Malignancies arising from the myeloid line include acute and chronic myelogenous leukemia, myelodysplastic syndromes, and myeloproliferative diseases. Those arising from the lymphoid line include lymphoma, lymphocytic leukemia, multiple myeloma, and WM. Chromosomal abnormalities – both point mutations and translocations – are common among hematological malignancies, have an established role in diagnosis, and are increasingly used in guiding specific approaches to treatment.

Waldenström's macroglobulinemia is a distinct B-cell lymphoproliferative disorder characterized by a lymphoplasmacytic infiltrate in the bone marrow and high levels of a monoclonal immunoglobulin M (IgM) in the serum [6,7]. The disease can have a chronic, indolent course, with patients remaining asymptomatic for years. The principal complications include:

- Manifestations of the monoclonal gammopathy, including symptomatic hyperviscosity, cryoglobulinemia, and cold agglutinin disease.
- Disease-related cytopenia.
- Bulky adenopathy or organomegaly.
- Severe neuropathy.
- Amyloidosis.
- Disease transformation.

